**Phase 1b Dose-Finding Portion of Part 1: Cycle 1 Day 3**

Blood samples will be collected at the following time points on Cycle 1 Day 3 for all Cohort 1 patients enrolled in the Phase 1b dose-finding portion of Part 1 of the study: predose (0 hour; prior to dosing of G1T28) and at 0.5 (EOI of G1T28), 1, 1.5 (EOI of etoposide), 2, 2.5, 3.5, 4.5, 6.5, 8.5 (optional time point, if approved by the sponsor in advance), and 24.5 hours postdose (relative to the start of G1T28 infusion). Collection of PK blood samples in additional cohorts of the Phase 1b dose-finding portion of Part 1 is optional. The EOI sample for G1T28 should be drawn 2 to 5 minutes prior to the EOI. The EOI samples for G1T28 and etoposide must be drawn after completing infusion of the drugs and the actual times at which the samples were drawn should be documented. Time window parameters noted above for Cycle 1 Day 1 also apply to Cycle 1 Day 3. The Cycle 1 Day 3 sampling scheme is summarized in [Table 11-2](#).

**Table 11-2 Day 3 of Cycle 1 Blood Sampling Scheme Based on Predicted Administration Times of G1T28 and Etoposide**

Sample	1	2	3	4	5	6	7	8	9	10	11
Sample Time (h)	0 (Predose a )	0.5 b (G1T28 EOI)	1	1.5 (Etop EOI)	2	2.5	3.5	4.5	6.5	8.5 (optional c )	24.5

EOI = end of infusion; Etop = etoposide; h = hour

Times are approximate. For simplicity, assumptions were based on 0.5 hour increments. Actual times will be recorded and may vary from those listed here.

- a Predose is defined as prior to dosing of G1T28.
- b The EOI sample for G1T28 should be drawn 2 to 5 minutes prior to the EOI.
- c 8.5 hour sample (optional time point, if approved by the sponsor in advance)

**Pharmacokinetic Parameters**

Pharmacokinetic parameters to be derived from G1T28, etoposide, and carboplatin plasma concentration-time data are presented in [Table 11-3](#).

**Table 11-3 Pharmacokinetic Parameters**

$C_{max}$	The observed peak plasma concentration determined from the plasma concentration vs. time data
$T_{max}$	The time to reach the observed peak plasma concentration from the plasma concentration vs. time data
$AUC_{0-t}$	Area under the plasma concentration-time curve from 0 to t hours after dosing, calculated by linear/log trapezoidal method
$\lambda_z$	Terminal phase rate constant, determined by linear regression of at least 3 points on the terminal phase of the log-linear plasma concentration-time curve. The correlation coefficient ( $r^2$ ) for the goodness of the fit of the regression line through the data points has to be 0.80 or higher, for the value to be considered reliable.
$t_{1/2}$	Terminal half-life, defined as $0.693$ divided by $\lambda_z$
$AUC_{0-\infty}$	Area under the concentration-time curve from time-zero extrapolated to infinity, calculated as: $AUC_{inf} = AUC_{last} + \frac{C_{last}}{\lambda_z}$ where $C_{last}$ is the last quantifiable concentration in the terminal elimination phase.
CL	Clearance after intravenous administration, calculated as: $CL = \frac{Dose}{AUC_{inf}}$
$V_z$	Volume of distribution in the terminal elimination phase, calculated as: $V_z = \frac{CL}{\lambda_z}$

Pharmacokinetic samples may also be obtained from additional patients depending on the outcome of initial PK analysis.

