Following a single 30-minute IV infusion of G1T28, the median time to reach the maximum concentration (Tmax) ranged between 0.25 and 0.47 hour after the start of infusion. The maximum concentration (Cmax) increased in a dose-proportional manner following a single 30-minute IV infusion of G1T28 over the dose range of 6 to 192 mg/m^2. Total systemic (area under the concentration-time curve [AUC]) exposure increased more than dose proportionally over the dose range of 6 to 192 mg/m^2 of G1T28. The elimination kinetics of G1T28 appeared to follow a 3-compartment model. The geometric mean half-life (t1/2) was 12.9 to 14.7 hours for the 48 to 192 mg/m^2 dose levels. The interpatient variability (%CV) of the PK parameters at the 192 mg/m^2 dose level was low (<15%). The PK of G1T28 suggests that drug accumulation following repeated administration is unlikely to occur. Urinary excretion appears to be a minor route of elimination for unchanged G1T28.

G1T28 showed positive pharmacodynamic effects in 2 assays. Dose-dependent inhibition of ex vivo whole blood stimulation occurred following a single IV infusion of G1T28 at 96 and 192 mg/m^2 (maximum mean inhibition of 37.2% and 60%, respectively, occurred 4 hours

after the end of infusion). Lymphocyte proliferation started to recover 8 hours after the end of infusion, but inhibition of proliferation persisted until the last sampling time point of 24 hours. Assessment of bone marrow 24 hours after administration of G1T28 at the biologically effective dose (BED) of 192 mg/m^2 revealed a significant decrease in the number of HSPCs in the synthesis (S)/gap 2 (G2)/mitosis (M) phases of the cell cycle (ie, an increase in the proportion of cells in G1 arrest). This G1 arrest persisted in the different progenitor lineages 32 hours after dosing. However, no changes were noted in the peripheral blood counts, indicating that the bone marrow arrest is transient and reversible and is consistent with the effects seen in animals.

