#### 4.3.2. Pharmacokinetic Studies

Pharmacokinetic studies in rats and dogs showed that the relationship between dose level and plasma exposure to G1T28 was generally similar between males and females and did not change with repeated daily dosing. Exposure to G1T28 increased with dose level, but not always proportionally. Plasma half-life values for G1T28 after IV administration were approximately 4 hours in rats and dogs.

In vitro analyses of direct and time-dependent inhibition suggest that drug interactions based on inhibition of cytochrome P40 (CYP)1A2-, 2B6-, 2C8-, 2C9-, 2C19-, and 2D6-mediated metabolic pathways are unlikely at concentrations of G1T28 below 100  $\mu\text{M}$  (44,600 ng/ml). Drug interactions based on G1T28 mechanism-based inhibition of CYP3A4-mediated metabolic pathways are possible. Additionally, in vitro induction studies of the 3 major inducible CYP enzymes (CYP1A2, CYP3A4, and CYP2B6) in human hepatocytes suggest that G1T28-mediated induction is unlikely.

While etoposide is a CYP3A4 substrate, there are no specific label warnings regarding coadministration with CYP3A4 inhibitors. This may in part be due to the relatively equal contributions of renal and hepatic clearance to the total clearance of etoposide. In addition, administration of oral ketoconazole, a potent CYP3A4 and uridine disphosphate glucuronosyltransferase 1 family, polypeptide A1 (UGT1A1) inhibitor, with oral etoposide for 3 of every 5-week cycles resulted in an increase of the median AUC of oral etoposide of only 20% and did not alter its toxicity profile ([Yong 2007](#)). In the present Study G1T28-02, IV G1T28 will be administered prior to IV etoposide on Days 1 to 3 of 21-day cycles in patients with adequate renal function. In the Phase 1b dose-finding portion of Part 1 of the study, PK of etoposide, carboplatin, and G1T28 will be assessed on Days 1 and 3 of the first cycle. In addition, frequent CBCs will be assessed. Since myelotoxicity is the major toxicity of etoposide, this will be monitored closely in this study.

In vitro inhibition studies with membrane transporter model systems also suggest G1T28 is unlikely to cause a drug-drug interaction (DDI) based on inhibition of breast cancer resistance protein (BCRP)-, bile salt export pump (BSEP)-, organic anion transporter

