### **8.6. Prior and Concomitant Medications and Procedures**

All concomitant medications including prescription medications, over-the-counter preparations, growth factors, blood products, and parenteral nutrition taken during the 14 days before the date of enrollment, during the study treatment, and through 30 days after the last dose of study drug will be documented. Documentation will include information regarding start and stop dates, dose(s), and reasons for the medication use.

Administration of other concomitant nonprotocol anticancer therapies prior to progression is not permitted while on this study.

Administration of other concomitant investigational agents for any indication is not permitted while on this study.

Concomitant radiation therapy treatment for SCLC will be regarded as disease progression, and is not permitted while on this study.

Caution should be exercised when administering etoposide phosphate with drugs that are known to inhibit phosphatase activities (eg, levamisole hydrochloride). Although carboplatin has limited nephrotoxic potential, caution should be exercised when administering carboplatin with aminoglycosides, which has resulted in increased renal and/or audiologic toxicity. Any medication that is contraindicated when using etoposide or carboplatin is not permitted, and special warnings and precautions for use of carboplatin and etoposide should be observed.

Necessary supportive care such as antiemetics, antidiarrheals, etc., per the standard of care at the study center will be permitted. **Administration of hematopoietic growth factors in Cycle 1 will not be permitted (ie, no growth factors should be used prior to the actual Cycle 2 Day 1 dosing visit).** However, hematopoietic growth factors may be utilized in subsequent cycles at the investigator's discretion as stated in Section 8.4.4.2. To reduce potential immune system interactions, the use of dexamethasone as an antiemetic should be minimized where possible.

G1T28 is a time-dependent inhibitor of CYP3A4 and is a substrate for CYP3A4. G1T28 exposure may be altered by concomitant use of drugs that are strong CYP3A inhibitors or inducers. The exposure of drugs that are CYP3A substrates may be altered by concomitant use of G1T28 (Section 4.3.2).

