### **13.7. Pharmacokinetic Analysis**

Pharmacokinetic analyses will be based on the PK set, and all analysis and reporting of plasma concentration and PK parameter data will be performed separately for each analyte.

During Part 1 of the study, serial blood samples will be collected on Days 1 and 3 of Cycle 1 to determine G1T28, etoposide, and carboplatin plasma concentrations. Plasma concentration data will be tabulated descriptively and graphed at each visit and time point. Pharmacokinetic parameters will be calculated with noncompartmental methods (WinNonlin Version 6.3 or higher) based on the plasma concentration-time data. The following PK parameters will be calculated (when data permit their calculation):  $C_{max}$ ,  $T_{max}$ ,  $AUC_{0-t}$ ,  $AUC_{0-\infty}$ ,  $t_{1/2}$ ,  $CL$ , and  $V_z$ . Pharmacokinetic parameters will be summarized descriptively by visit and analyte. If applicable, G1T28 plasma concentration and PK parameters will also be summarized by dose level.

Exploratory PK modeling and simulations may also be performed.

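### The protocol's single-dose clearance formula, applied on Day 3, makes G1T28 clearance too low because Day 3 AUCinf still contains drug from the Day 1 and Day 2 doses

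*Protocol*

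**What the plan says.** Protocol Section 11.2 applies Table 11-3 to G1T28, etoposide and carboplatin alike. The table has three linked entries:

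- AUC0-∞: "Area under the concentration-time curve from time-zero extrapolated to infinity", as AUClast + Clast/λz.
- CL: "Clearance after intravenous administration, calculated as" Dose/AUCinf.
- Vz: "Volume of distribution in the terminal elimination phase, calculated as" CL/λz.

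No entry names a sampling day, corrects for a predose concentration or offers a multiple-dose alternative. Section 13.7 states that "serial blood samples will be collected on Days 1 and 3 of Cycle 1", lists CL and Vz among the parameters to be calculated, and adds: "Pharmacokinetic parameters will be summarized descriptively by visit and analyte".

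Under Section 8.1, G1T28 and etoposide are given on Days 1, 2 and 3 of each cycle and carboplatin on Day 1 only. Section 4.2 reports that the G1T28 half-life "was 12.9 to 14.7 hours for the 48 to 192" mg/m² dose levels. The same section describes 3-compartment elimination and expects little accumulation on repeat dosing.

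On interactions, Section 8.6 states: "G1T28 is a time-dependent inhibitor of CYP3A4 and is a substrate for CYP3A4". Section 4.3.2 states: "Drug interactions based on G1T28 mechanism-based inhibition of CYP3A4-mediated metabolic pathways are possible". It then discusses etoposide as a CYP3A4 substrate and refers to the Day 1 and Day 3 PK sampling. SAP Section 6.2.10 leaves PK analysis to a separate document.

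**The concern.** Dose/AUCinf equals clearance only if all the drug in the AUC came from that one dose. Day 1 meets this condition: nothing was given before, and the synopsis places the 24.5 h sample before the Day 2 dose. Day 3 does not. Its curve and extrapolated tail carry whatever remains of the Day 1 and Day 2 doses, while the numerator is still a single dose. The error has the same sign in every patient, so averaging does not remove it.

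The Day 1 and Day 3 profiles are the only scheduled repeat-dose PK in these documents; the Phase 1a data in Section 4.2 are single-dose. The protocol does not name auto-inhibition. It does describe G1T28 as both a time-dependent inhibitor and a substrate of CYP3A4, so a fall in G1T28 clearance by Day 3 is something a reader would look for. A formula that produces such a fall when clearance has not changed makes the Day 3 value hard to interpret. The PK profiles of G1T28, and of etoposide given with it, are secondary objectives (Table 5-1).

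**Working it through.** The plan states no accumulation ratio or expected Day 3 clearance, so there is no figure of its own to reproduce.

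**Inputs from the protocol.** Half-life t½ of 12.9 to 14.7 h (4.2). Dosing interval τ of 24 h nominal, at most 28 h (8.1). Sampling times from Tables 11-1 and 11-2.

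**Assumptions.** Linear PK; true clearance unchanged from Day 1 to Day 3; only the terminal phase remains 24 h after a dose. Let f be the share of single-dose AUCinf in the terminal phase. The documents do not give f, so it is varied from 0 to 1.

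**Step 1, carry-over.** The residue of a dose given kτ earlier is f × r_k, with r_k = 2^(−kτ/t½). At τ = 24 h:

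- t½ 12.9 h: r1 = 0.275, r2 = 0.076, r3 = 0.021
- t½ 14.7 h: r1 = 0.322, r2 = 0.104, r3 = 0.034

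**Step 2, bias of the stated formula.** Day 3 AUCinf ÷ single-dose AUCinf = 1 + f(r1 + r2), and CL bias = 1/[1 + f(r1 + r2)] − 1.

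| f | AUCinf ratio (12.9 h / 14.7 h) | Day 3 CL bias |
|---|---|---|
| 0 | 1.000 / 1.000 | 0% |
| 0.25 | 1.088 / 1.107 | −8.1% / −9.6% |
| 0.50 | 1.176 / 1.213 | −14.9% / −17.6% |
| 0.75 | 1.263 / 1.320 | −20.8% / −24.2% |
| 1 (one compartment) | 1.351 / 1.426 | −26.0% / −29.9% |

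At τ = 28 h the ceiling is −21.4% to −25.3%.

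**Step 3, the planned sampling times.** A noncompartmental simulation used the linear/log trapezoid, λz from the last three samples, assumed early half-lives of 0.3 and 2 h, and the non-terminal AUC split equally between those two phases. For f = 0.25 to 0.75, Day 3/Day 1 CL was 0.75 to 0.92. Vz behaved differently: its ratio was 0.78 to 0.81 at f = 0.75, 0.89 to 0.90 at f = 0.5, and 1.01 to 1.02 at f = 0.25. The reason is that the apparent half-life rose by 3% to 13%.

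**Step 4, etoposide.** No half-life is stated. Under assumed one-compartment half-lives of 4, 6, 8 and 12 h, the same formula gives a maximum CL bias of −1.6%, −6.2%, −12.3% and −23.8%. Carboplatin has no Day 3 dose, so a Day 3 CL does not apply to it.

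**Step 5, the alternatives.** By superposition, Day 3 AUC0-24 equals the single-dose AUC0-72, which is AUCinf × (1 − f·r3). Dose/AUC0-24 is therefore off by 1/(1 − f·r3) − 1: +0.5% to +0.8% at f = 0.25 and +2.1% to +3.5% at f = 1. Subtracting the decaying predose concentration gives a CL ratio of 1.00 when the true terminal rate is used. With λz taken from the last three Day 3 samples, the simulation for f = 0.25 to 0.75 gives 0.95 to 0.98. Dose/AUC0-24, interpolated from the same samples, gives 0.97 to 0.99 of the noncompartmental Day 1 CL.

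**Step 6, which ratio answers which question.** With clearance unchanged, Day 3/Day 1 AUC0-24 = (1 − f·r3)/(1 − f·r1). That is 1.07 to 1.08 at f = 0.25, 1.15 to 1.17 at f = 0.5 and 1.35 to 1.43 at f = 1, so it rises through accumulation alone. Day 3 AUC0-24 over Day 1 AUCinf is 1 − f·r3, which stays between 0.97 and 1.00.

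**The case against.** Table 11-3 is a generic list of definitions, and the operative PK analysis sits in a document not supplied. It may already specify a dosing-interval clearance for Day 3. That stands: the documents show a rule that is wrong as written for Day 3, not that biased values will be reported.

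The 3-compartment profile and the expectation of little accumulation both point below the one-compartment ceiling. That also stands. They limit the size of the bias but do not make the formula valid.

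The carry-over would be visible. A Day 3 predose sample is taken, concentrations are tabulated, and AUC0-t with a last sample at 24.5 h is close to a dosing-interval AUC. This helps a careful reader, but it does not correct the CL and Vz columns.

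Four stronger readings are tempting, and the documents do not support them:

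- A reader might infer that Vz falls by the same factor as CL and also mimics inhibition. Vz depends on the apparent λz and can come out unbiased (Step 3). Reduced clearance lowers CL and λz together and leaves Vz about unchanged.
- A reader might set the bias against the protocol's 20% band. That band applies to the initial cohort's mean AUC0-24.5h for dose adjustment (Section 6.1.1.2). No dose rule uses Day 3 CL.
- A reader might infer that the study would declare a false interaction. The analysis is descriptive, with no interaction test or threshold.
- A reader might infer a distorted etoposide interaction result. G1T28 precedes etoposide on Day 1 too, so Day 1 is not an inhibitor-free baseline, and the etoposide carry-over may be trivial.

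**Conclusion.** The point holds for G1T28 clearance. As written, Table 11-3 with Section 13.7 yields a Day 3 CL that is too low under linear PK, in the direction CYP3A4 auto-inhibition would take. The size cannot be fixed from the documents: about 8-10% if a quarter of single-dose AUC is terminal, 15-18% if half is, never more than 26-30%, and approaching zero with that share. The ceiling should not be quoted as the expected bias.

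For etoposide the formula error is the same but its size is unknown. Day 3 Vz rests on an unreliable CL; beyond that, no direction or size can be claimed for it. Whether any of this reaches a report depends on the separate PK plan. It is a modest correction, worth making because it is cheap and because the Day 1 to Day 3 contrast is the only scheduled repeat-dose PK described.

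**What to change.** In Table 11-3 and Section 13.7, or in the separate PK plan:

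1. Restrict CL = Dose/AUCinf, and Vz derived from it, to Day 1.
2. For Day 3 G1T28 and etoposide, compute CL = Dose/AUC over the 24 h dosing interval, interpolating to 24 h after the start of that drug's own infusion. Alternatively, use AUCinf minus Cpredose/λz, stating that this assumes the residue declines at the terminal rate.
3. Report Day 3/Day 1 AUC0-24 as an accumulation ratio only.
4. To look for a change in clearance, compare Day 3 AUC0-24 with Day 1 AUCinf.
5. State that no Day 3 CL is derived for carboplatin.

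The cost is a few lines of text. The scheduled samples, including the Day 3 predose sample, and the planned software are sufficient. If the PK plan already contains these rules, a cross-reference from Table 11-3 is enough.

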### 11.3. Safety Assessments

Safety evaluations will be conducted at baseline and throughout the study. Safety evaluations will include monitoring of AEs, vital signs measurements, physical examinations, ECGs, clinical laboratory studies, infusion-related reactions, tumor response based on RECIST, Version 1.1 (see Section 11.5), PFS, and overall survival.

The toxicity of G1T28 administered IV with chemotherapy will be assessed by the investigators using the NCI CTCAE, Version 4.03.

### 11.3.1. Adverse Events and Serious Adverse Events

#### 11.3.1.1. Definition of Adverse Event

An AE is defined as any untoward medical occurrence in a patient administered a medicinal product that does not necessarily have a causal relationship with this treatment. An AE can, therefore, be any unfavorable and unintended sign (including an abnormal laboratory finding), symptom, or disease temporally associated with the use of a medicinal (investigational) product, whether or not related to the study (investigational) product.

An abnormal laboratory value is not an AE unless it is considered to be clinically significant.

Adverse events include the following:

- All suspected adverse drug reactions (ADRs)
- All reactions from medication overdose, abuse, withdrawal, sensitivity, or toxicity
- Apparently unrelated illnesses, including the worsening of a pre-existing illness (see pre-existing conditions below)
- Injury or accidents (Note that if a medical condition is known to have caused the injury or accident [eg, a fall secondary to dizziness], the medical condition [dizziness] and the accident [fall] should be reported as 2 separate AEs). The outcome of the accident (eg, hip fracture secondary to the fall) should be recorded under comments.
- Abnormalities in physiological testing or physical examination (findings that require clinical intervention or further investigation beyond ordering a repeat [confirmatory] test)
- Laboratory abnormalities that are clinically significant and require clinical intervention or further investigation (beyond ordering a repeat [confirmatory] test) unless they are associated with an already reported clinical event. Laboratory abnormalities associated with a clinical event (eg, elevated liver enzymes in a patient with jaundice) should be described under comments on the report of the clinical event rather than listed as a separate AE.

An AE does not include:

- Medical or surgical procedures (eg, surgery, endoscopy, tooth extraction, transfusion); the condition that leads to the procedure will be an AE
- Pre-existing diseases or conditions present or detected at the start of the study that do not worsen
- Situations where an untoward medical occurrence has not occurred (eg, hospitalization for elective surgery, social, and/or convenience admissions)
- Overdose of either study drug or concomitant medication without any signs or symptoms
- Disease progression

An unexpected AE is any AE that is not identified in nature, severity, or frequency in the current Investigator Brochure or product information.

- An unexpected ADR is an adverse reaction, the nature or severity of which is not consistent with the applicable product information (eg, IB for an unapproved investigational medicinal product). All noxious and unintended responses to a medicinal

product related to any dose should be considered ADRs. The phrase “responses to a medicinal product” means that a causal relationship between a medicinal product and an AE is at least a reasonable possibility, ie, the relationship cannot be ruled out. All serious and unexpected ADRs will have expedited reporting to the regulatory agencies following the International Conference on Harmonisation (ICH) requirements

It is the responsibility of the investigator to document all AEs that occur during the study and every effort should be made to remain alert to possible AEs. Patients should be encouraged to report AEs spontaneously or in response to general, nondirected questioning. Adverse events should be reported on the appropriate page of the eCRF.

In the event of an AE, the primary concern is the safety of the patient. If necessary, appropriate medical intervention should be provided, and the investigational drug discontinued.

